### 10.2.2 Concomitant therapies

The purpose of imputing concomitant therapy / antihypertensive therapy dates is only to assign a concomitant therapy to a specific treatment phase for the summary tables. No imputed date is considered in the medical evaluation of a concomitant therapy / antihypertensive therapy.

**Table 8 Imputation rules for an incomplete or missing concomitant therapy or antihypertensive therapy date**

Field	Incomplete date	Missing date
Concomitant therapy / Antihypertensive therapy end date	The upper limit.	No imputation; the therapy is considered as ongoing.
Concomitant therapy / Antihypertensive therapy start date	
The rules below apply in the order presented:
 
 
1. If the (imputed) end date is on or after the start of the <study treatment> and if the start of the <study treatment> falls within the upper and lower limits (inclusive), the <study treatment> start date is used.
 
2. If the end date is missing and the <study treatment> start date falls within the upper and lower limits (inclusive) the <study treatment> start date is used.
 
3. In all other cases the lower limit is used.
 
 
If the concomitant therapy is flagged as PRIOR TO FIRST DOSE and the start date is completely missing; the <study treatment> start date – 1 day is used.
	Whichever is the earlier of the concomitant therapy / Antihypertensive therapy end date or <study treatment> start date.

Depending on the analysis, <study treatment> is SB placebo, DB, SB aprocitentan or DB-WD treatment.

After applying the rules above, it may be that a concomitant medication can be allocated to multiple study parts. In that case, it will be allocated one study part according to the following priority: (1) DB part, (2) DB-WD part, (3) SB aprocitentan part and (4) RI period.

## 11 CHANGES OR CLARIFICATIONS TO ANALYSES PLANNED IN THE STUDY PROTOCOL

In other efficacy endpoints [section 6.1.3 of the protocol]:

- Discontinuation of randomized study treatment due to confirmed grade 3 (i.e., mean SiSBP/SiDBP  $\geq$  180/110 mmHg, respectively) hypertension [see section 6.1.3 of the protocol, version 2, [D-18.214](#)]

is replaced by [Section [6.5.1](#) of this SAP]: Discontinuation of study treatment due to lack of efficacy.

Also, in other efficacy endpoints [section 6.1.3 of the protocol]:

- Ratios to baseline for all assessed time points of DB, SB and DB-WD parts in UACR

is replaced by [Section [6.5.1](#) of this SAP]:

- Ratios to baseline for all assessed time points in the DB and SB aprocitentan parts and ratios to DB-WD baseline (Week 36) for all assessed time points in the DB-WD part in UACR.

In the supportive analyses for the primary endpoint [section 10.3.2.4 of the protocol] LOCF and BOCF analyses were added [Section [6.2.5](#) of this SAP]. In the supportive analyses for the key secondary endpoint [section 10.3.3.4 of the protocol] a BOCF analysis was added [Section [6.3.5](#) of this SAP].

In the SAP Version 1 and protocol, the baseline for the DB-WD part was referred to as 'Week 36'. It has now been renamed to 'DB-WD baseline (Week 36)' and defined as the last assessment before or on the day of re-randomization which may be *before* Week 36.

Analysis of AESIs was added to the SAP.

Specifications and analyses related to the COVID-19 pandemic were added to the SAP [[D-20.063](#)].

The estimand strategy was changed from that laid out in the protocol [version 3, [D-20.008](#)], following comments from regulatory agencies. In brief, the treatment policy strategy is now used for the main estimands, whereas the hypothetical strategy is now used for supplementary estimands.

In detail: in the description of statistical analyses [section 10.3 of the protocol, version 3, [D-20.008](#)], for the main analyses in the DB and DB-WD parts, it was specified that:

- AOBPM measurements obtained after premature discontinuation of DB or DB-WD treatment will be excluded from this analysis (i.e., considered as missing), leading to a hypothetical strategy estimand in the terminology of [[ICH E9 \(R1\)](#)].

This was replaced by [see Section 6.2.2 and 6.3.2 of this SAP]:

- All AOBPM measurements obtained after premature discontinuation of DB or DB-WD treatment or the addition/dose increase of a diuretic will be included in the main analysis, leading to a treatment policy strategy estimand in ICH terminology [ICH 2017b].

A hypothetical strategy estimand will be used in sensitivity analyses [see Sections 6.5.1 and 6.3.4 of this SAP].

Endpoints related to BP control and response were added as exploratory endpoint [see Sections 6.5.1 and 6.5.2 of this SAP].

## 12 LIST OF TABLES, LISTINGS AND FIGURES

The list of Tables, Listings and Figures is available in Idorsia's Electronic Document Management System.

## 14 APPENDICES

### 14.1 Revision history

Version Date	Version	Implemented Change(s)
05-JUL-2018	1.0	Draft 1
15-NOV-2018	2.0	Draft 2
04-APR-2019	1	Final Version 1
23-SEP-2021	2	
 
• Section 1: Indicate protocol amendment and addendum related to the COVID-19 pandemic.
 
• Section 2.1: Update added on the recruitment.
 
• Section 2.4: Section added on the impact of the COVID-19 pandemic.
 
• Section 4.1.6 and 4.17: Clarifications added on the PPS and mPSS sets.
 
• Section 4.1.8 and 4.1.9: Clarifications added on the aFAS and maFAS sets.
 
• Section 4.1.10 and 4.1.12: Actual treatment received definitions added for SAF and mSAF sets.
 
• Section 4.1.13: Clarification added on the PK set.
 
• Section 5.1.2 and 5.1.3: Summaries added for discontinuation reasons study/treatment related to the COVID-19 pandemic.
 
• Section 5.2: Summaries added by study part for all PDs and important PDs and specific summaries related to the COVID-19 pandemic.
 
• Section 5.3: Summary added for subjects excluded from the PK set.
 
• Section 5.4.1: Region definition finalized based on final list of participating countries, BMI category added as a demographic variable.
 
• Section 5.4.2: Clarification of the variables included in the disease characteristics.
 
• Section 5.4.4: Clarifications added on the definitions of previous and concomitant therapy.
 
• Section 5.5.1: Clarifications added for treatment duration calculation.
 

		
 
• Section 5.5.2: Calculation of compliance updated if bottle not returned.
 
• Section 6.2.2: Clarifications added on the intercurrent events.
 
• Section 6.2.4: Sensitivity analysis added for possible exclusion of site data.
 
• Section 6.2.6: Added subgroups analyses for efficacy.
 
• Section 6.2.7: Section added on the impact of COVID-19 pandemic on the analysis of primary endpoint.
 
• Section 6.3.4: Sensitivity analysis added for possible exclusion of site data.
 
• Section 6.3.7: Section added on the impact of COVID-19 pandemic on the analysis of key secondary endpoint.
 
• Section 6.4.1: Clarification added on the ABPM valid reading specifications.
 
• Section 6.5.2 and 6.5.3: Home SBP/DBP added as another efficacy endpoint to analyze.
 
• Section 7.1.1.6: Section added for AESIs.
 
• Section 7.4.2: Summary added for ECG findings.
 
• Section 7.6.1: Clarification added on the definitions and exposure-adjusted MACE/MACE-plus incidence rates added.
 
• Section 7.6.3: Updated analysis for biomarker. Biomarker analysis moved from efficacy (Section 6.8) to safety (Section 7.6.3).
 
• Section 8.1: General rules for data presentation updated.
 
• Section 10.1.2: Adjustment and clarification for time window added.
 
• Section 10.2.2: Clarification added on the imputation rules.
 
• Section 11: Explanation added on the changes from protocol.
 
• Section 14: Definitions added in the appendices.
 

06-APR-2022	3	
 
• Section 1: Indicate the change of primary estimand following comments from regulatory agencies.
 
• Section 4.1.6 and 4.1.7: Definitions update for PPS and mPPS.
 
• Section 4.1.13: Clarifications added for PK set.
 

	

• Section 5.1.1: Clarifications on eligibility criteria summaries.

• Section 5.4.1: Age and BMI categories adapted. Body weight category added.

• Sections 5.4.2: Categorization added for number of antihypertensive therapies present at screening.

• Section 5.4.4: Deletion of concomitant therapies summary present at baseline and descriptive table of individual antihypertensive therapies stopped or ongoing during screening period added.

• Section 5.5.2: Interruptions moved from Section 5.1.3 to 5.5.2 and additional details provided.

• Section 6.2.2: Change of estimand strategy.

• Section 6.2.4: Hypothetical strategy estimand will be used for sensitivity analysis.

• Section 6.2.6: Subgroups updated or added.

• Section 6.3.2: Change of estimand strategy.

• Section 6.3.4: Hypothetical strategy estimand will be used for sensitivity analysis.

• Section 6.3.6: Subgroups updated or added.

• Section 6.5.1: BP control and response as exploratory endpoints.

• Section 6.5.2: Addition of analysis specification for BP control and response.

• Section 6.6: Update of table summary for efficacy analyses due to change of estimand strategy.

• Section 7.1.2: Addition of analyses for time to (first) oedema/fluid retention.

• Section 7.3.2: Addition of other thresholds for the marked abnormalities tables.

• Section 8.2.2: Adjustment of code for multiple imputation.

• Section 8.2.5: New code added for control/response endpoints.

• Section 10.1.2: Time window changed and clarified.

• Section 14.4: Specifications added for antihypertensive medications.

--	--

## 14.2 Thresholds for marked abnormalities

Parameter	LL	LLL	HH	HHH	HHHH
Hematology					
Hemoglobin	< 100 g/L	< 80 g/L	Increase in > 20 g/L above ULN or above baseline if baseline is above ULN	Increase in > 40 g/L above ULN or above baseline if baseline is above ULN	
Hematocrit	< 28% in women < 32% in men	< 20%	> 55% in women > 60% in men	> 65%	
Platelet count	< $75 \times 10^9/L$	< $50 \times 10^9/L$	> $600 \times 10^9/L$	> $999 \times 10^9/L$	
Leukocyte count	< $3.0 \times 10^9/L$	< $2.0 \times 10^9/L$	> $20.0 \times 10^9/L$	> $100.0 \times 10^9/L$	
Neutrophils	< $1.5 \times 10^9/L$	< $1.0 \times 10^9/L$	NA	NA	
Eosinophils	NA	NA	> $5.0 \times 10^9$	NA	
Lymphocytes	< $0.8 \times 10^9/L$	< $0.5 \times 10^9/L$	> $4.0 \times 10^9/L$	> $20 \times 10^9/L$	
Blood Chemistry					
AST (U/L)	NA	NA	> $3 \times ULN$	> $5 \times ULN$	> $8 \times ULN$
ALT (U/L)	NA	NA	> $3 \times ULN$	> $5 \times ULN$	> $8 \times ULN$
Alkaline Phosphatase	NA	NA	> $2.5 \times ULN$	> $5 \times ULN$	
Bilirubin Total ( $\mu\text{mol/L}$ )	NA	NA	> $2 \times ULN$	> $5 \times ULN$	
Creatinine	NA	NA	> $1.5 \times ULN$ or > $1.5 \times$ baseline if baseline > ULN	> $3 \times ULN$ or > $3 \times$ baseline if baseline > ULN	

Parameter	LL	LLL	HH	HHH	HHHH
Glucose	< 3.0 mmol /L	< 2.2 mmol /L	> 8.9 mmol /L	> 13.9 mmol /L	
Sodium		< 130 mmol/L	> 150 mmol/L	> 155 mmol/L	
Potassium	< 3.2 mmol/L	< 3.0 mmol/L	> 5.5 mmol/L	> 6.0 mmol/L	
Urate	NA	NA	> 590 µmol/L	> 720 µmol/L	
Albumin	< 30 g/L	< 20 g/L	NA	NA	
eGFR	< 60 mL/min/1.73m 	< 30 mL/min/1.73m 	NA	NA	
Cholesterol	NA	NA	>7.76 mmol/L	>10.34 mmol/L	
Triglyceride	NA	NA	>1.69 mmol/L	>3.39 mmol/L	

ALT = alanine aminotransferase; AST = aspartate aminotransferase; eGFR = estimated glomerular filtration rate; NA = not applicable; ULN = upper limit of normal.

Baseline = last assessment before randomization, also in the analysis of the DB-WD part.

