### 6.2.6 Subgroup analyses for the primary endpoint

The following subgroups will be considered.

- Age at screening (18–< 65, 65–< 75 and  $\geq 75$  years).
- Sex (male/female).
- Weight at baseline ( $\leq 100$  kg,  $> 100$  kg).
- BMI at screening  $< 30$ ,  $30$ –<  $40$  and  $\geq 40$  kg/m^2.
- Race (Black or African American, White, Asian, Other\*).
- Region (Asia/Australia, Europe, North America, as defined in Section 5.4.1).
- UACR at Baseline ( $< 30$  mg/g,  $30$ – $300$  mg/g,  $> 300$  mg/g.,
- CKD stage at baseline (1–2 defined as eGFR  $\geq 60$  mL/min/1.73 m^2, 3–4 defined as eGFR  $15$  to  $< 60$  mL/min/1.73 m^2).
- Diabetes as per medical history (Y/N) (defined as Hyperglycaemia/new onset diabetes mellitus [SMQ]).
- Protocol Version 1/2 vs protocol Version 3 at randomization. Note: in protocol Version 3, beta-blockers were counted as antihypertensive medications at Screening, which was not the case in Version 1/2.

\* The 'Other' category will not be considered for subgroup analyses due to the mix of races and small number of subjects limiting the ability (i.e., low power) to detect differences between treatment groups. 'Other' includes American Indian or Alaska Native, Native Hawaiian or other Pacific Islander and Other.

If the size of a subgroup is lower than 25 subjects, subgroup categories might be pooled.

The aim of the subgroup analyses is to explore the consistency of treatment effect in relevant subgroups. Results of the subgroup analyses will be displayed in a forest plot and will include:

- An estimate of the treatment effect for each aprocitentan dose vs placebo with its 95% CI for each level of the subgroup. It will be calculated as the LSM difference vs placebo at Week 4 obtained separately for each subgroup level as described for the main analysis [Section 6.2.3] but using 95% rather than 97.5% CIs.
- A p-value for the interaction test obtained from the mixed model for the main analysis extended with factors for the subgroup, treatment by subgroup interaction and treatment by subgroup by visit interaction, with appropriate contrasts.
- A vertical reference line displayed at the level of the overall treatment effect.

The study is not designed or powered to detect interactions but an arbitrary two-sided significance level of 0.10 will be used for the interpretation of the interaction test. No multiplicity adjustment is applied as these subgroup analyses are exploratory in nature.

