### 7.1 Adverse events

#### 7.1.1 Variables

##### 7.1.1.1 Treatment-emergent adverse events

The original terms used by the investigators to describe AEs in the **Adverse Events** eCRF are assigned a PT and a SOC for classification and tabulation using MedDRA (last available version).

Subjects who experienced the same AE more than once within a specified time period (as qualified by the same PT) are counted only once.

An event/assessment is treatment-emergent if the onset/assessment date is between the start date of the randomized treatment period up to EOT+30 days (begin and end dates included). More in particular:

- An event/assessment is DB treatment emergent if the onset/assessment date is between the start date of the DB part up to the day before the start date of the SB treatment part (or EOT + 30 days if the subject did not enter the SB part);

- An event/assessment is SB treatment emergent if the onset/assessment date is between the start date of the SB aprocitentan part up to the day before the start date of the DB-WD treatment part (or EOT + 30 days if the subject did not enter the DB-WD part);
- An event/assessment is DB-WD treatment emergent if the onset/assessment date is between the start date of the DB-WD part up to EOT + 30 days.

An event/assessment with an onset/assessment date between the start date of the run-in period up to the start of randomized treatment period (if the subject is randomized; EOT if the subject is not randomized) will be designated as run-in-emergent.

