### 7.3.2 Analysis

Changes from baseline for laboratory tests to visits in the DB+SB part will be summarized using descriptive statistics by visit and treatment group (in the DB part). Changes from DB-WD baseline (Week 36) to visits in the DB-WD part and up to EOS will be summarized by visit and treatment group (in the DB-WD part). Data will be displayed in SI units whenever possible and graphical approaches will be applied for certain variables.

Percentage changes from baseline in plasma volume to visits in the DB+SB part will be estimated based on baseline (V4) as well as post-baseline (Vx) in hemoglobin and hematocrit (as a fraction between 0 and 1) using the following formula [[Strauss 1951](#)]:

$$\text{estimated change} = 100 \times \frac{\text{hemoglobin (V4)}}{\text{hemoglobin(Vx)}} \times \frac{1 - \text{hematocrit (Vx)}}{1 - \text{hematocrit(V4)}} - 100$$

Percentage changes from Week 36 (V11) in plasma volume to visits in the DB-WD part will be estimated similarly but with V4 replaced by V11. Estimated changes in plasma volume will be summarized by visit and treatment group (in the DB+SB part or DB-WD part, where appropriate).

The number (%) of subjects with laboratory marked abnormalities will be tabulated by study part (DB, SB, and DB-WD) and treatment group (within study part). In addition, the number (%) of subjects with AST or ALT > 3 × the ULN combined with bilirubin > 2 × ULN will be tabulated. In addition, AST or ALT > 5 or 10 × ULN will also be tabulated.

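### The eGFR marked-abnormality flags have no baseline condition, so stable pre-existing CKD is tabulated as treatment-emergent

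*SAP*

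**What the plan says.** The rule has to be assembled from several places in the SAP.

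- **Thresholds (Section 14.2).** eGFR has a first low flag at "< 60 mL/min/1.73m"² and a second at "< 30 mL/min/1.73m"². Neither carries a baseline condition. In the same table, creatinine switches to a multiple of the subject's own value, "baseline if baseline > ULN", and high haemoglobin is handled in a similar way.
- **Treatment-emergence (Section 7.1.1.1).** "An event/assessment is treatment-emergent if the onset/assessment date is between the start date of the randomized treatment period up to EOT+30 days". The rule for each study part is also by date. Nothing requires the value to be new or worse than before treatment.
- **Values used (Section 7.3.1).** Scheduled and unscheduled assessments both count.
- **Output (Section 7.3.2).** "The number (%) of subjects with laboratory marked abnormalities will be tabulated by study part", for the DB, SB and DB-WD parts, and by treatment group within each.
- **Population.** Section 6.2.6 plans a subgroup on "CKD stage at baseline (1–2 defined as eGFR" of at least 60, against stages 3–4 at 15 to < 60. Section 5.4.2 has baseline eGFR categories of < 30, 30–< 45, 45–< 60 and ≥ 60. The protocol addendum, Section 2.1.2, makes provision for subjects with eGFR between 15 and 30.
- **Baseline (footnote to Section 14.2).** "Baseline = last assessment before randomization, also in the analysis of the DB-WD part".

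**The concern.** A count of treatment-emergent abnormalities is normally read as what happened after treatment began. For eGFR, this table mixes two groups: subjects who crossed the cut-off on study and subjects who were below it on arrival. The plan expects the second group, since it defines a subgroup and baseline categories for them.

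Two things are at stake. First, the reported percentages overstate how often renal function became abnormal. This is hardest to correct for in the SB part, where everyone receives aprocitentan 25 mg and no concurrent placebo column shows the background. Second, in the DB part the subjects already below the cut-off add roughly equal numbers to every arm, which pulls the ratio between arms towards 1. The SAP adjusts creatinine, the companion renal measure, for an abnormal baseline but not eGFR.

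**Working it through.** **Step 1: apply the rule to single subjects.** The column for what happens assumes that the subject has at least one eGFR value in the part.

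| Baseline eGFR | On study | < 60 flag | < 30 flag | Real worsening? |
|---|---|---|---|---|
| 45 | stays 45 | yes, in each part entered | no | no |
| 55 | falls to 35 | yes | no | yes |
| 45 | falls to 25 | yes | yes | yes |
| 25 | stays 25 | yes, in each part entered | yes, in each part entered | no |
| 70 | falls to 55 | yes | no | yes |

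The first two rows give the same result although only one subject got worse. The < 30 flag is uninformative only for subjects who were already below 30. For a subject who starts at 30 to < 60, it needs a real fall.

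**Step 2: illustrate the size.** The plan gives no figure to reproduce: no share of subjects below 60 at baseline and no expected rate of eGFR abnormalities. The inputs below are therefore assumptions.

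- q = share with baseline eGFR < 60: 10%, 20%, 30%
- r = share of those with at least one on-treatment value < 60: 1, with 0.9 as a check
- p = new onset below 60 among subjects starting at ≥ 60: 5% on placebo, 10% on active

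Tabulated proportion = q × r + (1 − q) × p.

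With r = 1:

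| q | Placebo | Active | Ratio | Difference | Already < 60, as share of flagged placebo subjects |
|---|---|---|---|---|---|
| 10% | 0.10 + 0.90 × 0.05 = 14.5% | 0.10 + 0.90 × 0.10 = 19.0% | 1.31 | 4.5 points | 0.10/0.145 = 69% |
| 20% | 0.20 + 0.80 × 0.05 = 24.0% | 0.20 + 0.80 × 0.10 = 28.0% | 1.17 | 4.0 points | 0.20/0.240 = 83% |
| 30% | 0.30 + 0.70 × 0.05 = 33.5% | 0.30 + 0.70 × 0.10 = 37.0% | 1.10 | 3.5 points | 0.30/0.335 = 90% |

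Among subjects starting at ≥ 60, the same inputs give 5% versus 10%: ratio 2.00, difference 5.0 points.

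With r = 0.9 the tabulated ratio is 1.33 at q = 10% and 1.11 at q = 30%, so the result depends little on every such subject staying flagged.

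**Step 3: read the two scales separately.** The absolute difference shrinks only by the factor (1 − q). The ratio and the meaning of each percentage suffer much more.

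**Step 4: the SB part.** The SB layout in Section 8.1 is a single aprocitentan 25 mg column. The DB+SB layout splits SB by earlier randomized group, but all of those subjects are on 25 mg. With q = 20% and new onset of 10%, the table would show 28%, with no concurrent arm to reveal that 20 of the 28 points were present at entry.

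**The case against.** The case for leaving the table alone has real substance.

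- **Other outputs carry the signal.** Section 7.3.2 summarizes laboratory changes from baseline by visit and arm, and eGFR is among the tests in Section 7.3.1. The creatinine flag is baseline-referenced above ULN, and eGFR is computed from creatinine. Section 5.4.2 tabulates baseline eGFR categories by arm, so a reader can see how many started low. All safety data are listed. This stands as partial mitigation. It is partial because visit summaries can average out individual falls, the creatinine flag needs more than a 1.5-fold excess over ULN or baseline, and the baseline table is planned for the FAS and mFAS, not for the set used in the SB part.
- **Absolute thresholds are common in this table.** Most parameters in Section 14.2 have them, and choosing them for a descriptive count is largely convention. That is fair. eGFR differs in that the plan itself expects subjects beyond the cut-off at entry.
- **The table is not tested.** Table 5 leaves its statistical-analysis cell empty, so power or z-statistics for it would describe a test that nobody plans. This stands, and none are offered here.
- **Simply dropping subjects already below 60 loses information.** A fall from 55 to 35 would then appear in no eGFR flag. This stands, and a baseline condition alone is not enough.

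A reader might infer that all stage 3–4 subjects are flagged at both levels in every part, or that a renal effect would be hidden in this trial. The documents support neither. Stage 3 subjects reach the < 30 flag only by worsening, a flag arises only in parts entered with a value below the cut-off, and the outputs above remain. Nor can the absence of a shift table be asserted beyond the SAP text: the main protocol was not among the documents reviewed, and Section 12 keeps the list of outputs elsewhere.

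**Conclusion.** The point holds, but narrowly. As written, the descriptive marked-abnormality table counts stable pre-existing CKD as treatment-emergent: at < 60 for anyone who enters below 60, and at < 30 only for those who enter below 30, in each part where such a value is recorded. The percentages are inflated, and the DB between-arm ratio is diluted.

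The direction follows from the rules. The size does not, because it depends on a baseline CKD share and incidence rates that the documents do not give. Under the assumptions above (10–30% below 60 at entry, all still flagged, new onset 5% versus 10%), the ratio drops from 2.0 to 1.31–1.10 and the difference from 5.0 to 4.5–3.5 points. No primary or key secondary conclusion is affected. This is a worthwhile improvement to one safety table, not a flaw in the trial.

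**What to change.** In Sections 7.3.2 and 14.2:

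1. Count an eGFR flag as treatment-emergent only when the category is new or worse than at baseline. The denominator is subjects not already in that category: baseline ≥ 60 for the < 60 flag, and baseline ≥ 30 for the < 30 flag.
2. Add a shift table, by study part and treatment group, of worst on-treatment eGFR category against the baseline categories of Section 5.4.2 (< 30, 30–< 45, 45–< 60, ≥ 60). A fall from 55 to 35 then stays visible as a move from 45–< 60 to 30–< 45.
3. For DB-WD, keep the pre-randomization baseline that the Section 14.2 footnote states. If DB-WD baseline is preferred, amend that footnote explicitly. The choice matters: with DB-WD baseline, a subject who first fell below 60 during the SB part and is still below it at Week 36 leaves the DB-WD count.

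The cost is one added condition in the derivation and one extra table, from data already collected. The downsides are that denominators differ by flag and that falls within a single category still show only in the change-from-baseline summaries and listings.
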